#### 4.2 SCIENTIFIC RATIONALE FOR STUDY DESIGN

*To evaluate the effects of our experimental manipulation, we need an active control group for this RCT study design. The RT has been used as a control condition in many previous published studies and is an*

*accepted control intervention. Thus, we use it as a control condition in our study design. There are no known or potential problems associated with the control group.*

#### 4.3 JUSTIFICATION FOR INTERVENTION

*The chosen 10-sessions of experimental manipulation - IBMT has been shown to improve behavior, cognition, and brain in previous RCTs in healthy adults. Thus, we choose to use the same setup and design, and expect the same length and frequency of the intervention would be appropriate for adults with polysubstance use.*

#### 4.4 END-OF-STUDY DEFINITION

A participant is considered to have completed the study if he or she has completed the baseline assessment, 10 intervention sessions, and post-intervention assessment.

### 5 STUDY POPULATION

#### 5.1 INCLUSION CRITERIA

In order to be eligible to participate in this study, an individual must meet all of the following criteria:

1. At least 18 years old
2. Free of any psychiatric diagnoses or medication (besides a SUD to alcohol, tobacco, or cannabis)
3. In the past month, at least 4 episodes of heavy episodic drinking; at least 3 occasion of cannabis use; and daily cigarette use for at least the past month
4. Normal or corrected-to-normal vision
5. Written informed consent
6. No previous meditation or neurofeedback experiences

#### 5.2 EXCLUSION CRITERIA

An individual who meets any of the following criteria will be excluded from participation in this study:

1. Any psychiatric diagnoses other than an SUD
2. Medical disorder(s) that may affect the central nervous system; medications that affect the central and autonomic nervous system; or a positive pregnancy test result (females)
3. Excluding cannabis, evidence of recent (past month) illicit drug use.

#### 5.3 LIFESTYLE CONSIDERATIONS

N/A

#### 5.4 SCREEN FAILURES

Screen failures are defined as participants who consent to participate in this study but are not subsequently assigned to the study intervention or entered in the study. Individuals who do not meet the criteria for participation in this trial (screen failure) because of meeting one or more exclusion criteria that are likely to change over time may be rescreened. Examples include the successful removal of metal

devices that previously made them ineligible for an MRI scan. Rescreened participants will be assigned the same participant number as for the initial screening.

## 5.5 STRATEGIES FOR RECRUITMENT AND RETENTION

*We anticipate to enroll 70 participants (males and females) who are at least 18 years old across different race and ethnicity based on local demographic characteristics. Subjects will be recruited through print and media ads within local community. This will include radio and online ads and recruitment through social media. Flyers will be distributed throughout the local community. Based on our and other's previous experiences in longitudinal studies, about 5-10% of participants will dropout over the study period due to illness or relocation. We plan a dropout rate of 20% for this brief intervention given the population is polysubstance users. We propose to recruit 70 adults of which 56 (80%) will complete the study.*

*Compensation and Retention. Participants will be financially compensated with \$300 in total for completing the study protocol (approximately for 15 hours of time); participants who only partially complete the protocol will be compensated based on prorated hours. To maximize participant retention we will maintain contact with participants over time via frequent assessment intervals (e.g., requiring a functioning phone number and email address to contact participants by phone or email as needed, and obtaining the name, address, and phone number of at least 2 friends or classmates who can provide contact information for the participants, should we be unable to contact them during the study; emails and reminder phone calls prior to all study visits; offer flexible scheduling options for assessment (including weekends); provide fair compensation to participants; and maintain positive relations with participants. These procedures were used to maintain adequate participant retention in our prior NIH studies.*

## 6 STUDY INTERVENTION(S) OR EXPERIMENTAL MANIPULATION(S)

### 6.1 STUDY INTERVENTION(S) OR EXPERIMENTAL MANIPULATION(S) ADMINISTRATION

#### 6.1.1 STUDY INTERVENTION OR EXPERIMENTAL MANIPULATION DESCRIPTION

*Experimental Manipulation – IBMT (Arm 1): IBMT emphasizes the cooperation between body and mind in facilitating and achieving a meditative state ecologically. Each IBMT session is facilitated by an experienced coach who has demonstrated the ability to attain the appropriate state of body and mind, and to lead the group to achieve a similar state. The coach creates a harmonious and relaxed atmosphere, observes facial and body cues to identify those who are struggling with the method, and gives proper feedback for effective practice. IBMT coach helps subjects attain desired state by first providing a brief period to induce a cognitive or emotional state that will facilitate the training. Then, coach helps subjects find an appropriate and balanced body posture and follow instructions to achieve deeper levels of relaxed body (physiology of relaxation) and experience a restful feeling and mental quiet (psychology of relaxation) mindfully. When the mind wanders, the coach helps subjects accept and be open to experiences without judgment, and further guides subjects to use a favorite mental image as a tool to return to the present moment gently. At last, the coach facilitates a brief group discussion to ensure subjects having positive experiences consistent with the intent of IBMT. The method stresses no effort to control thoughts, but instead emphasizes a state of restful alertness that allows a high degree of awareness of the body, mind, and environment.*

*Control Intervention – RT (Arm 2): For RT, each session includes pre-, post- and practice sessions, similar to IBMT procedure and is facilitated by a trained coach. However, RT involves relaxing different muscle groups over the face, head, shoulders, arms, legs, chest, back, and so on, guided by the experienced and certified coach. With eyes closed and in a sequential pattern, one concentrates on the sensation of relaxation, such as feelings of warmth and heaviness. Therefore, RT includes relaxation and imagery (no mindfulness component) and could serve as an ideal active control. Along with other groups, we have been using RT as active control in our RCTs.  The progressive training helps achieve physical and mental relaxation and calmness.*

#### 6.1.2 ADMINISTRATION AND/OR DOSING

*Both arms of interventions will be administered face-to-face as a group by trained interventionists. Both interventions will have 10 group sessions, and the completion of all 10 sessions is considered to be having a “full-dose” intervention. Participants in the same arm/group will interact with a shared interventionist.*

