### 4 STUDY DESIGN

#### 4.1 OVERALL DESIGN

*The study is a randomized control trial (RCT) involving two groups – IBMT (Arm 1: experimental manipulation) and RT (Arm 2: control group) group. Participants in each group will be assessed at baseline and post-intervention using behavioral and brain assessments as described in Section 1.3. Automatic randomization will be conducted by study staff and used to assign participants to each arm/group condition using an algorithm before the baseline assessment. This randomization procedure ensures balance between groups on gender while also balancing total treatment numbers.*

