### 6.3 MEASURES TO MINIMIZE BIAS: RANDOMIZATION AND BLINDING

*To minimize potential biases, participants are randomized based on automatic covariate conducted by Co-I using an adaptive algorithm. Participants are blinded to the intervention. Specifically, they were told that they will be engaged in body-mind intervention, without knowing whether or not the intervention they received is the experimental manipulation or control intervention. See methods of analysis in **Section 9, Statistical Considerations** for details on randomization. Additionally, research staff who assesses participants are also blinded of the participants' intervention condition. Randomization code is maintained by the Co-I. A planned breaking of randomization code and blinding would occur for any participants who reported serious adverse events. The PI and Co-I will identify which group the participant is in, without the need for research staff to be involved in knowing the participant's intervention group.*

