#### 9.2 SAMPLE SIZE DETERMINATION

*Our RCT design is focused on determining if within-person brain changes significantly differ across the intervention groups. All participants in this study will be those who use polysubstance. In prior work involving smokers (N = 27), we detected significant fMRI signal changes in the ACC/mPFC (Cohen's  $d = .90$ ) after 2-wk of IBMT than before IBMT . Compensating for the expected variability of findings in ACC/mPFC activity in polysubstance use, we thus expect a conservative, medium to large (Cohen's  $d = .80$ ) effect (i.e., we expect the effect size between the intervention and control conditions to be 0.80 at post-intervention) based on ours and other studies. However, we may expect polysubstance users to be somewhat more variable. Given the power considerations, we increased our sample size to 35 per group, which will give us 90% power to detect fMRI signal changes evoked by IBMT. The target sample size for the proposed study in the R61 phase (n = 70; 35/condition) is designed to provide sufficient evidence to detect significant brain changes in ATC users following interventions. Given we anticipate up to 20% attrition across the R61 phase of the study, power analysis suggests adequate power.*

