### 9.4.2 ANALYSIS OF THE PRIMARY ENDPOINT(S)

*The primary endpoints are brain assessments and are all repeated measures assessed at baseline and post-intervention. For brain assessment of brain assessment of functional activity, whole-brain analyses of fMRI timeseries during resting state will be calculated and for all endpoints based on standardized processing pipelines of fMRI data using REST software ([www.restfmri.net](http://www.restfmri.net)). After these data preprocessing and calculation, numerical values will be generated for each brain voxel. Next, the effects of intervention (IBMT vs. RT) on primary endpoints will be examined using repeated-measures ANOVA with time x group interaction effect. Threshold-free cluster enhancement approach will be used to identify clusters showing significant effects. Variance and covariance across repeated measures will be calculated as part of the ANOVA. Age and sex will be included as covariates to control for potential confounding effects of age and sex on brain outcomes. Results will be presented as F values for the interaction effect, along with p values to indicate statistical significance. Normality and homogeneity of variance assumptions will be checked using SPSS built-in tools for ANOVA. Multiple comparison corrections will be conducted using FDR correction. Missing data will be handled with case-wise deletion.*

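### Training is delivered in groups with a shared coach, but the ANOVA and the 90% power treat participants as independent; if change correlates within training groups, standard errors will be too small

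*Combined protocol and SAP*

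**What the plan says.** Section 6.1.2 has both arms "administered face-to-face as a group by trained interventionists", over 10 group sessions, and adds: "Participants in the same arm/group will interact with a shared interventionist". Section 6.1.1 has the IBMT coach bring the group to a similar state and close each session with a group discussion.

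Allocation is by individual. In section 6.3, "participants are randomized based on automatic covariate conducted by Co-I using an adaptive algorithm". In section 4.1, randomisation is "used to assign participants to each arm/group condition using an algorithm before the baseline assessment".

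In section 9.4.2 the arm effect is "examined using repeated-measures ANOVA with time x group interaction effect", with age and sex as covariates. The only covariance mentioned is within person: "Variance and covariance across repeated measures will be calculated as part of the ANOVA". There is no training-group or coach term. The clusters in "Threshold-free cluster enhancement approach will be used to identify clusters showing significant effects" are clusters of voxels and have nothing to do with training groups.

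Section 9.2 takes d = 0.80 between arms at post-intervention and 35 per arm, "which will give us 90% power to detect fMRI signal changes evoked by IBMT". It gives no ICC, group size or design effect. Section 9.4.1 adds nothing on clustering.

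**The concern.** Randomising individuals makes the arms comparable at the start, but it does not keep outcomes independent afterwards. People who share ten sessions, a coach and a discussion may change together, and section 6.1.1 describes a mechanism by which they could. If they do, each participant carries less information about the arm effect than the ANOVA assumes. Its p values and intervals are then too optimistic.

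The test at risk is the primary one. Section 9.4.1 presents this phase as the step before full-scale R33 trials, so an over-confident result, or the lack of any ICC estimate, would carry into that design. The sections cited do not call for training-group or coach identifiers, so the assumption might not be checkable afterwards.

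Coach allocation is a related gap. Section 4.1 uses arm and group interchangeably, so section 6.1.2 can be read as one coach per arm. But it also speaks of interventionists in the plural, and section 6.2.1 sets one list of coach criteria for both arms. With one coach per arm, no model can separate coach from arm.

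**Working it through.** **Inputs from the documents.** 35 per arm and d = 0.80 (section 9.2); 56 of 70 completing, so 28 per arm (section 5.5).

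**Assumptions.** Two-sided 5% level (none is stated). Equal, closed training groups of m = 4 (7 per arm) or m = 7 (4 per arm). ICC of change 0.01, 0.05 or 0.10. Section 1.3 puts the baseline scan on Day 1 and the next training visit at about Day 3, which makes large groups hard to fill. Groups of 4 are therefore the more plausible case, but this is an inference.

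**1. The plan's own figure.** Noncentrality = 0.80 / √(2/35) = 3.35 on 68 df, which gives power of 91.0%. This agrees with the stated 90%, with all 70 analysed and independent.

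**2. Design effect.** DEFF = 1 + (m − 1) × ICC. The true standard error is √DEFF times the naive one.

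**3. Type I error of the naive test.** An approximation is 2 × [1 − Φ(1.96/√DEFF)]. For m = 7 and ICC 0.05, √1.30 = 1.14, 1.96/1.14 = 1.72, and the result is 8.6%. The simulated values below are for a two-sample t test on change (54 df, no true effect, 1,000,000 runs per cell):

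| m | ICC | DEFF | Type I error | Part falsely favouring IBMT (nominal 2.5%) |
|---|---|---|---|---|
| 4 | 0.01 | 1.03 | 5.3% | 2.7% |
| 4 | 0.05 | 1.15 | 6.8% | 3.4% |
| 4 | 0.10 | 1.30 | 8.6% | 4.3% |
| 7 | 0.01 | 1.06 | 5.7% | 2.9% |
| 7 | 0.05 | 1.30 | 8.6% | 4.3% |
| 7 | 0.10 | 1.60 | 12.3% | 6.2% |

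A t test on training-group means (12 or 6 df) stays at 5.0% throughout.

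**4. Power of an analysis that respects the groups.** At 28 per arm, ICC 0.05 and d of change 0.80, the noncentral t with variance multiplied by DEFF gives 73% (m = 4, 12 df) and 59% (m = 7, 6 df). With independent participants and 54 df it is 83.6%.

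Using 0.80 for change assumes a pre-post correlation r of 0.5, since d of change = 0.80/√(2(1 − r)). For r from 0.3 to 0.7, the 83.6% becomes 70% to 97%, the 73% becomes 58% to 91%, and the 59% becomes 46% to 81%.

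**5. What lost degrees of freedom do on their own.** With ICC exactly zero and d of change 0.80, about 8–9% (m = 4) or 18% (m = 7) of significant naive results are no longer significant on group means.

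**The case against.** The best reply is that the size is entirely assumed. The documents give no ICC or group size, and in groups of 4 at ICC 0.01 the false-positive rate moves only from 5% to 5.3%. That stands, and it is why the result is a range and the remedy is a sensitivity analysis.

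The phase is also an early-stage pilot. Section 6.2.1 supervises coaches and rates 10% of sessions, section 6.4 tracks attendance, and the Manual of Procedures mentioned in section 10.1.10, which is not among the documents, may set out group logistics. These are fair mitigations. But supervising delivery does not make participants in a group independent, and no section reviewed brings training group into the analysis.

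Section 1.3 counts days from each participant's own start, so entry may be rolling and groups may overlap. A simple nested effect would then not fit. This also stands, and the fix allows for it.

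A reader might infer more than the documents support:

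- *That the trial's false-positive rate is 9% or 12%.* Those figures are for one t test on a region mean under assumed values. The voxelwise TFCE/FDR procedure was not computed.
- *That clustering pushes results towards IBMT.* The excess splits equally between the arms.
- *That clustering leaves the trial underpowered or calls for a larger sample.* The fall from 91.0% to 83.6% comes from the planned 20% dropout. The naive t test at ICC 0.05 and 28 per arm still rejects about 82% (groups of 4) and 81% (groups of 7) of the time, partly because it is anti-conservative. The 73% and 59% are largely the price of the adjusted analysis.
- *That coach and arm are confounded.* Section 6.1.2 allows that reading but does not settle it.

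**Conclusion.** The concern holds in conditional form. The plan delivers both arms in groups, models only within-person covariance, and states a power that rests on independent participants. If change is positively correlated within training groups, the standard errors will be too small. Over the assumed range the type I error of a single region-mean test would be about 5.3% to 12.3% against a nominal 5%. The groups-of-4 figures (5.3% to 8.6%) are the more plausible ones, and the effect is minor at ICC 0.01. The result rests on assumed ICCs, equal closed groups, 28 completers per arm and a two-sided 5% level. It justifies a cheap improvement to the plan, with medium confidence, and not a redesign.

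**What to change.** 1. Record training-group ID and coach ID at every session.
2. In section 9.4.2 keep the planned primary analysis. Prespecify a sensitivity analysis of change in mean ACC/mPFC signal, with the mask fixed in advance and age and sex as covariates. Fit it twice to the same data: once without a training-group term, and once with a training-group random effect nested in arm and small-sample degrees of freedom. Report both estimates, standard errors and intervals, and the ICC with its interval.
3. Judge clustering only by comparing those two fits. Do not set the voxelwise result against the region-mean result, because that changes the outcome as well as the model. Do not treat loss of significance alone as lack of robustness, because step 5 of the working shows it occurs with no clustering at all.
4. If entry is rolling and membership overlaps, define the cluster term to match, for example by coach or by sessions shared.
5. Label the voxelwise p values as assuming independent participants.
6. In section 9.2 state that the 90% assumes independent participants and give a design-effect range, such as 1.03 to 1.60 for groups of 4 to 7 and ICC 0.01 to 0.10.
7. State how coaches are allocated. If they do not cross arms, say that the arm effect includes any coach effect, which no model can separate.

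The cost is some wording, two recorded variables and one added analysis. That analysis will have wider intervals, few degrees of freedom (hence the 73% and 59% power in step 4 of the working) and an imprecise ICC. At a true ICC of 0.05 a typical 95% interval is −0.13 to 0.39 with 7 groups of 4 per arm, or −0.08 to 0.45 with 4 groups of 7. The estimate is zero or negative about 37–38% of the time.

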### 6.2 FIDELITY

#### 6.2.1 INTERVENTIONIST TRAINING AND TRACKING

Explicit coach selection criteria and on-going monitoring and supervision of treatment delivery and fidelity will ensure that the interventions are of the highest quality, follow the protocols precisely, and prevent coach drift and contamination. For IBMT and RT, the coach must have a minimum of a master's degree in psychology, social work, or a related field and experience running group therapy. The coach will need to meet additional criteria: have completed the trainer course, had a daily practice of mindfulness, and attended a silent meditation retreat. To monitor coach's adherence and competence, all sessions will be recorded and a random sample of 10% will be rated by the investigators using the modified Adherence Scale to ensure the interventionist has adequate competence and adherence to the protocols, and to prevent drift.

### 6.3 MEASURES TO MINIMIZE BIAS: RANDOMIZATION AND BLINDING

*To minimize potential biases, participants are randomized based on automatic covariate conducted by Co-I using an adaptive algorithm. Participants are blinded to the intervention. Specifically, they were told that they will be engaged in body-mind intervention, without knowing whether or not the intervention they received is the experimental manipulation or control intervention. See methods of analysis in **Section 9, Statistical Considerations** for details on randomization. Additionally, research staff who assesses participants are also blinded of the participants' intervention condition. Randomization code is maintained by the Co-I. A planned breaking of randomization code and blinding would occur for any participants who reported serious adverse events. The PI and Co-I will identify which group the participant is in, without the need for research staff to be involved in knowing the participant's intervention group.*

### 6.4 STUDY INTERVENTION/EXPERIMENTAL MANIPULATION ADHERENCE

*Participants' adherence with study procedures will be tracked by taking their attendance at intervention visits. Moreover, in each session, we use participant self-report and coach observation to calculate study intervention adherence by the participant based on their engagement and quality of practice.*

## 6.5 CONCOMITANT THERAPY

N/A

### 6.5.1 RESCUE THERAPY

N/A

## 7 STUDY INTERVENTION/EXPERIMENTAL MANIPULATION DISCONTINUATION AND PARTICIPANT DISCONTINUATION/WITHDRAWAL

### 7.1 DISCONTINUATION OF STUDY INTERVENTION/EXPERIMENTAL MANIPULATION

If a clinically significant finding is identified (including, but not limited to changes from baseline) after enrollment, the investigator or qualified designee will determine if any change in participant management is needed. Any new clinically relevant finding will be reported as an adverse event (AE).

The data to be collected at the time of study intervention discontinuation will include the following:

- The reason(s) for discontinuing the participant from the intervention, and methods for determining the need to discontinue
- If the participant is due to complete assessments within 1 weeks of being discontinued from the study intervention, those assessments will be administered at the time of discontinuation; if the next scheduled assessments are more than 1 week from the discontinuation date, the next scheduled assessment will not be administered. Thereafter, the participant will be not included in all future scheduled assessments, as they did not participate in the intervention.

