### 1.2 SCHEMA

**Figure 1. Flowchart of screening, inclusion, and assessment process**

### 1.3 SCHEDULE OF ACTIVITIES

	Pre-screening	Visit 1 Day 1	Visit 2 to Visit 11 Day 3 ±1 to Day 30±1	Visit 12 Day 31 ±2	Visit 13 Day 90 ±2
Review Eligibility	X				
Informed Consent		X			
Demographics		X			
Outcome Evaluation					
Brain Assessment (MRI scan)		X		X	X
Cognitive Assessment (Self-control tasks)		X		X	X
Randomization		X			
Control & Experimental Interventions		X	X		
Adverse Events Reporting		X	X	X	X

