### 7.2 PARTICIPANT DISCONTINUATION/WITHDRAWAL FROM THE STUDY

Participants are free to withdraw from participation in the study at any time upon request.

An investigator may discontinue a participant from the study for the following reasons:

- Significant study intervention non-compliance, unless varying compliance is an aspect of the study objectives
- Lost-to-follow up; unable to contact subject (see **Section 7.3, Lost to Follow-Up**)
- Any event or medical condition or situation occurs such that continued collection of follow-up study data would not be in the best interest of the participant or might require an additional treatment that would confound the interpretation of the study
- The participant meets an exclusion criterion (either newly developed or not previously recognized) that precludes further study participation

The reason for participant discontinuation or withdrawal from the study will be recorded. Subjects who sign the informed consent form and are randomized but do not receive the study intervention may be replaced. Subjects who sign the informed consent form, and are randomized and receive the study intervention, and subsequently withdraw, or are discontinued from the study, will not be replaced.

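### Section 7.1 ends outcome scans when the intervention stops, so willing participants who stop more than a week before Visit 12 lose the primary endpoint by rule

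*Combined protocol and SAP*

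**What the plan says.** The rule is in the second bullet of protocol section 7.1 and has three parts.

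- Where an assessment is due within a week of discontinuation, "those assessments will be administered at the time of discontinuation".
- Otherwise, "if the next scheduled assessments are more than 1 week from the discontinuation date, the next scheduled assessment will not be administered".
- In either case, "Thereafter, the participant will be not included in all future scheduled assessments, as they did not participate in the intervention".

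Section 7.2 separately lets the investigator take a participant out of the study for "Significant study intervention non-compliance, unless varying compliance is an aspect of the study objectives". It also says that people who have received the intervention and then leave are not replaced.

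The schedule in section 1.3 places training at Visit 1 and at "Visit 2 to Visit 11 Day 3 ±1 to Day 30±1". MRI is at Visit 1, "Visit 12 Day 31 ±2" and "Visit 13 Day 90 ±2". The primary endpoint in section 3 is ACC/mPFC functional activity at baseline and post-intervention. Section 9.3 analyses only participants with all 10 sessions and complete primary data, under a modified intention-to-treat label. Section 9.4.2 deletes incomplete cases.

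**The concern.** Stopping the intervention and ceasing to be measured are different events, and section 7.1 merges them. Someone who stops attending sessions but would still come for a scan is not offered one. The reason given, that such people took no part in the intervention, does not fit a participant who attended several of the 10 sessions.

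The trial compares randomised arms at post-assessment (section 9.1). That comparison is protected when the endpoint is measured in everyone willing to be measured, whatever their attendance. If those who stop IBMT differ from those who stop RT, in number or in prognosis, the completers left in the two arms are no longer comparable groups.

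This is a data-collection problem and separate from the choice of analysis set. Sections 9.3 and 9.4.2 can be rewritten at any time before analysis, but a Day 31 scan that was not taken cannot be obtained later.

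**Working it through.** **1. The plan's own power figure.** Inputs from section 9.2 are d = 0.80 and 35 per arm. Alpha is not stated there, so I assume 0.05 two-sided. Power ≈ Φ(d·√(n/2) − 1.96).

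- n = 35: Φ(0.80 × √17.5 − 1.96) = Φ(1.387) = 91.7% (91.0% by the t distribution). The stated 90% reproduces.
- n = 28 completers per arm: Φ(0.80 × √14 − 1.96) = Φ(1.033) = 84.9% (t: 83.6%).

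**2. Who loses the scan.** The scan is withheld if the Visit 12 day minus the stop day exceeds 7.

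| Visit 12 held on | Stop days with no post scan | Share of the 30 training days |
|---|---|---|
| Day 29 | 1-21 | 21/30 = 70% |
| Day 31 | 1-23 | 23/30 = 77% |
| Day 33 | 1-25 | 25/30 = 83% |

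For the nominal Day 31 visit, stops on Days 24-30 bring the scan forward to the stop day. The window opens on Day 29, so scans on Days 24-28 fall 1-5 days before it. Scans on Days 29 and 30 are inside it.

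By sessions, assume ten evenly spaced sessions on Days 3, 6, …, 30. A participant discontinued on the day of any of sessions 1 to 7 (Days 3-21) gets no post scan. That is 7 of the 9 incomplete stopping points (78%). Someone with 7 of 10 sessions completed would be in this group.

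**3. How many people.** Section 5.5 states: "We propose to recruit 70 adults of which 56 (80%) will complete the study". That leaves 70 − 56 = 14 non-completers. If all 14 were intervention stoppers spread evenly over the 30 days (an assumption; the documents give no timing), 14 × 23/30 ≈ 11 would have no post scan. The range is 14 × 21/30 ≈ 10 to 14 × 25/30 ≈ 12. The remaining 3 or so would have a scan on the day they stopped.

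**4. Possible shift in an arm's mean.** The observed completer mean differs from the mean of all assigned by share of stoppers × (completer change − stopper change). The gap of 0.5-1.0 SD is assumed, as is the recoverable share of 10-20%.

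- Smallest: 0.10 × 0.5 = 0.05 SD, or 0.05/0.80 = 6% of the planned effect.
- Largest: 0.20 × 1.0 = 0.20 SD, or 0.20/0.80 = 25%.

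This is a one-arm figure. The bias in the between-arm contrast is the difference between the two arms' products of share and gap, and is zero if those products are equal.

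**5. What scanning stoppers would do to power.** Take 7 stoppers per arm, all scanned, so d = (28 × 0.80 + 7 × 0.80 × e)/35, where e is the fraction of the effect that stoppers obtain.

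- e = 1: d = 0.80, power 91.7%.
- e = 0.5: d = 0.72, power 85.4%.
- e = 0: d = 0.64, power 76.3%.

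Against 84.9% for completers only, power may rise or fall. The case for the change is validity of the comparison, not power.

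**The case against.** The strongest reply is that the rule does not alter the planned primary result. Section 9.3 keeps only 10-session completers, so a stopper's scan would be collected and then set aside. The hypothesis in section 9.1 is itself worded around completing the intervention. This stands to the extent that changing 7.1 alone achieves little; it has to be paired with 9.3 and 9.4.2. It does not justify withholding the scan, because completers of two different programmes are not randomised groups, and even a completer analysis needs stoppers' outcomes to test its robustness.

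Four stronger readings are tempting but not supported.

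- *Anyone who falls behind loses the scan.* The rule applies to people discontinued from the intervention. Section 7.3 has missed visits rescheduled, and a participant who skips a session without being discontinued keeps Visit 12.
- *An as-assigned or dropout sensitivity analysis becomes impossible.* Baseline scans, covariates and reasons for stopping would still allow imputation or tipping-point analyses. What is lost is observed outcomes to inform them.
- *All 14 losses are due to this rule.* Section 5.5 cites past dropout of 5-10% from illness or relocation, and some people will withdraw or be lost under any rule.
- *Every brought-forward scan is mistimed.* Scans on Days 29 and 30 lie inside the Visit 12 window.

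Nor do the documents show that stopping will differ by arm. They give no arm-specific rates, so this is a risk and not a forecast.

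**Conclusion.** The point holds. Section 7.1, read with the schedule in 1.3, makes the primary endpoint missing by design for participants discontinued more than a week before Visit 12. It scans some of the later stoppers outside the window, and no other section restores these assessments. An analysis by assigned arm could then include early stoppers only through imputation under assumptions that the data cannot test.

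The number of recoverable scans is at most 14 of 70. That most stoppers would lose the scan follows from the calendar only if stops are not concentrated in the last week. The shift of 0.05-0.20 SD in one arm's mean is an illustration on assumed inputs, and the net bias could be much smaller. The issue deserves attention now because the loss is permanent for each participant and the remedy is inexpensive.

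**What to change.** Replace the second bullet of section 7.1 with wording such as:

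> Participants who stop the intervention but have not withdrawn consent will be invited to the Visit 12 and Visit 13 assessments in their normal windows, whatever the number of sessions attended, unless a safety or eligibility ground in section 7.2 precludes it. A scan will be brought forward only for a participant who states that he or she will not return; its date will be recorded.

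In section 7.2, state that non-compliance with sessions does not by itself end outcome assessment. This concerns data collection only and leaves unchanged when anyone stops the intervention.

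In sections 9.3 and 9.4.2, add an analysis by assigned arm of all randomised participants with a post-intervention scan, at least as a sensitivity analysis, so that the added scans are used.

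The cost is a protocol amendment with IRB approval, plus at most 14 Visit 12 scans and the same number at Visit 13 beyond the 56 planned completers. The visits are already in the schedule, and section 5.5 already prorates compensation. The documents do not say how many scans are funded, so the budget should be checked. Visit 12 has priority, since Day 90 supports no stated endpoint. Some stoppers will decline.
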